### 7.2.5.3. Exploratory Endpoints

Change from baseline in exploratory efficacy variables will be summarized. Percent of patients in full clinical remission and incidence of ADA will be tabulated by treatments.

The slope of eGFR for the double-blind period will be estimated for each treatment and the slope of eGFR for the entire study period including the OLE will be analyzed. Other inferential statistics for exploratory efficacy variables may be presented as needed. Details will be described in the SAP.

## 7.2.6. Pharmacodynamic Analysis

Assessment of the PD effect of the treatment will be performed descriptively, including plotting graphically levels of serum C5 protein and CAP/CCP over time and relative to baseline levels. Inferential statistics may be generated as deemed necessary.

### **7.2.7. Pharmacokinetic Analysis**

Pharmacokinetic analyses will be conducted using noncompartmental methods. Pharmacokinetic parameters include, but will not be limited to: AUC,  $C_{max}$ ,  $T_{max}$ ,  $t_{1/2}$ , CL/F, V/F, cumulative amount excreted unchanged in urine (Ae), and percent of dose excreted (fe) in the urine of cemdisiran (25-mer) and 23-mer.

Other parameters may be calculated, if deemed necessary. Summary statistics and figures will be presented. Inferential statistics may be generated when deemed necessary.

### **7.2.8. Safety Analyses**

The primary parameter is the frequency of treatment-emergent AEs (hereafter referred to simply as AEs). Safety parameters also include vital signs, ECGs, clinical laboratory assessments, and physical exams. The extent of exposure will be summarized by treatment arm and overall.

AEs will be classified according to the Medical Dictionary for Regulatory Activities (MedDRA) System Organ Class and Preferred Term. Prior and concomitant medications will be classified according to the World Health Organization (WHO) drug dictionary. All SAEs occurring before the first dose of study drug and AEs related to study procedures will be listed. The number and percentage of patients experiencing AEs after the first dose of the study drug or events that worsened in severity after dosing will be summarized. AEs will be presented by maximum severity and relationship to study medication. SAEs and AEs leading to discontinuation of treatment will also be tabulated.

By-subject listings will be provided for deaths, SAEs, and AEs leading to study discontinuation. Frequency of AEs of clinical interest will also be summarized and by-subject listings will be provided.

Descriptive statistics will be provided for clinical laboratory data, 12-lead ECG interval data and vital signs data, presented as both actual values and changes from baseline over time.

Laboratory shift tables from baseline to worst values will be presented. Baseline will be defined as the last observation on or prior to Study Day 1.

Abnormal physical examination findings and 12-lead ECG data will be presented in a by-patient data listing. Details of any abnormalities will be included in patient listings.

Other safety summaries will be presented as appropriate. Further details will be specified in the SAP.

All safety analyses will be conducted using the Safety Analysis Set.

Additional data summaries to help understand any impact of COVID-19 on safety assessments will be outlined in the SAP.

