## Study Design

This is a multicenter, double-blind, placebo-controlled study comprised of three periods ([Figure 1](#)). The first period of the study is an observational 14-week run-in period during which patients' blood pressure, kidney function, degree of hematuria, and proteinuria will be measured. The standard of care is expected to remain unchanged during this run-in period. Patients will not receive study drug (cemdisiran or placebo) during this time. The second study period is a 36-week treatment period (defined as the time the first dose of study drug is administered on Study Day 1 through completion of the Week 36 assessments) which will evaluate the efficacy

and safety of subcutaneous (SC) cemdisiran compared to SC placebo in combination with standard of care in patients with IgAN and persistent proteinuria. The third period of the study is a 156-week optional open-label extension (OLE) period to further evaluate the long-term safety and clinical activity of cemdisiran. During the OLE, all patients (including those initially on placebo) will be treated with cemdisiran in combination with standard of care.

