### **6.3. Baseline Assessments (Treatment Period)**

Prior to dosing on Day 1, patients will be reassessed for eligibility, and blood and urine samples for clinical laboratory assessments and exploratory analyses collected, including blood samples for complement activity tests (CAP/CCP), C5 analysis, PK, ADA, CIC, and anti-Gd-IgA1 antibodies.

In addition, prior to administration of study drug, the following assessments will be performed: full physical examination, body weight and height, vital signs, ECG, urine pregnancy test, eGFR assessment, spot urine, and urinalysis.

Collection of blood and urine samples for PK analysis on Day 1 will be performed as outlined in [Table 5](#).

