### **6.7.1. Vital Signs**

Vital signs will be measured as specified in the Schedule of Assessments ([Table 1](#), [Table 2](#), [Table 3](#), and [Table 4](#)) and include blood pressure, heart rate, body temperature, and respiratory rate. Vital signs will be measured in the seated or supine position, after the patient has rested comfortably for at least 10 minutes. On Day 1, vital signs will be collected predose (no more than 4 hours prior to dosing) and 4 hours ( $\pm 30$  minutes) postdose. On all other dosing days, vital signs will be collected predose.

Blood pressure should be taken using the same arm throughout the study. Body temperature in degrees Celsius will be obtained via oral or tympanic method. Heart rate will be counted for a full minute and recorded in beats per minute, and respiration rate will be counted for a full minute and recorded in breaths per minute.

Additional vital sign assessments, as medically indicated, may be added at the discretion of the Investigator, or as per DMC advice.

Vital signs results will be recorded in the eCRF.

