### **6.7.4. Electrocardiogram**

Twelve-lead ECGs reporting rhythm, ventricular rate, RR interval, PR interval, QRS duration, and QT interval and Fridericia-corrected QT interval will be obtained, as specified in the Schedule of Assessments ([Table 1](#), [Table 2](#), [Table 3](#), and [Table 4](#)). Patients should be supine for at least 5 minutes before each ECG is obtained. A single 12-lead ECG will be performed at Screening. At all other time points, 12-lead ECGs will be performed in triplicate, with readings

1 minute apart. 12-lead ECGs will be performed predose (on the same day as dosing); 60 minutes ( $\pm 15$  minutes) postdose; and 4 hours ( $\pm 30$  minutes) postdose in relation to the Day 1 and Week 32 cemdisiran or placebo doses.

When ECG and blood sample collection occur at the same time, ECGs should be performed before blood samples are drawn.

The Investigator or qualified designee will review all ECGs to assess whether the results have changed since the Baseline visit and to determine the clinical significance of the results. These assessments will be recorded on the eCRF. Additional ECGs may be collected at the discretion of the Investigator, or as per DMC advice.

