#### **6.7.5. Clinical Laboratory Assessments**

The following clinical laboratory tests will be evaluated by a central laboratory. However, to assess patient eligibility at the end of the run-in period, eGFR will also be assessed locally. Specific instructions for transaminase elevations are provided in Section 5.2.3.1. For any other unexplained clinically relevant abnormal laboratory test occurring after study drug administration, the test should be repeated and followed up at the discretion of the Investigator, or as per DMC advice, until it has returned to the normal range or stabilized, and/or a diagnosis is made to adequately explain the abnormality. Additional safety laboratories and assessments as indicated by the clinical situation may be requested. Clinical laboratory assessments are listed in [Table 7](#) and include: hematology, serum chemistry and urinalysis parameters. Parameters will be assessed as specified in the Schedule of Assessments ([Table 1](#), [Table 2](#), [Table 3](#), and [Table 4](#)).

While local laboratory results may be used for urgent clinical and dosing decisions, on the day of the clinic visit assessments, all laboratory assessments specified in [Table 7](#) which are measured locally should also be sent in parallel to the central laboratory. In the case of discrepant local and central laboratory results on samples drawn on the same day, central laboratory results will be relied upon for clinical and dosing decisions. If central laboratory tests are not feasible due to COVID-19 restrictions, local laboratory tests for safety monitoring can be performed with approval from the Sponsor.

Clinical laboratory assessments may be collected at the clinical study site or at a location other than the study site (eg, at home) by a trained healthcare professional. On dosing days blood samples will be collected predose.

For any safety event or laboratory abnormality, additional laboratory assessments, imaging, and consultation may be performed for clinical evaluation and/or in consultation with the Medical Monitor; results may be collected and should be included in the clinical database.

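### The safety baseline rule in Section 7.2.8 has no pre-dose condition, so read literally it takes the 4-hour post-dose Day 1 value as baseline for vital signs and ECG intervals

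*Protocol*

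**What the plan says.** Section 7.2.8 of the Protocol contains a single baseline definition for the safety analyses: "Baseline will be defined as the last observation on or prior to Study Day 1". It sets no condition relative to dosing. The paragraph before it says that descriptive statistics will cover laboratory data together with "12-lead ECG interval data and vital signs data, presented as both actual values and changes from baseline over time".

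The first dose falls on Study Day 1. The Study Design section of the synopsis defines the treatment period as "the time the first dose of study drug is administered on Study Day 1 through completion of the Week 36 assessments".

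Three sections fix what is measured on that day:

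- Section 6.7.1, vital signs: "On Day 1, vital signs will be collected predose (no more than 4 hours prior to dosing) and 4 hours" after the dose, with a window of ±30 minutes.
- Section 6.7.4, ECG: "12-lead ECGs will be performed predose (on the same day as dosing); 60 minutes" (±15 minutes) and 4 hours (±30 minutes) "postdose in relation to the Day 1 and Week 32 cemdisiran or placebo doses". ECGs are triplicate at every time point except Screening.
- Section 6.7.5, laboratory: "On dosing days blood samples will be collected predose".

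Section 6.3, which describes the baseline assessments of the treatment period, states that "prior to administration of study drug, the following assessments will be performed: full physical examination, body weight and height, vital signs, ECG" and other items.

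**The concern.** A baseline for a safety change score should be free of study drug. A rule that accepts any observation on Day 1 achieves this only for measures taken solely before the dose that day. Vital signs and ECGs are not such measures, because both are deliberately repeated after the first dose.

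At stake is the interpretation of changes in QTcF, heart rate and blood pressure. If the baseline already contains whatever the first dose did within about 4 hours, the Day 1 post-dose assessment cannot show it and later changes are measured from a shifted origin. Only the cemdisiran arm can carry a drug effect, so the comparison between arms would shift as well.

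**Working it through.** The plan gives no figure to reproduce. The check applies the rule of Section 7.2.8 literally to the Day 1 schedule.

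**Step 1. Which value does the rule select?**

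| Measure | Day 1 times | Last observation on Day 1 | Pre-dose? |
|---|---|---|---|
| Vital signs (6.7.1) | pre-dose; +4 h ± 30 min | +4 h, that is 3.5 to 4.5 h after dosing | No |
| ECG intervals (6.7.4) | pre-dose; +60 min ± 15 min; +4 h ± 30 min | +4 h triplicate, 3.5 to 4.5 h after dosing | No |
| Laboratory blood samples (6.7.5) | pre-dose | pre-dose | Yes |

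The rule selects a post-dose baseline for vital signs and ECG in every patient who completes the Day 1 schedule, and an acceptable baseline for laboratory data.

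**Step 2. What does that do to the change scores?** Let B be the true pre-dose value, d the acute drug effect 4 hours after the first dose, and e the true drug effect at some other assessment. Assume that effects add and ignore measurement noise.

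- Pre-dose baseline: change = (B + e) − B = e.
- Literal rule: change = (B + e) − (B + d) = e − d.

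The error is −d at every assessment. The cases are:

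- Day 1, +4 h: the value is compared with itself, so the change is 0 whatever d is.
- Day 1, +60 min: e₁ − d, where e₁ is the effect at 60 minutes. An earlier post-dose value is compared with a later one.
- Effect persists (e = d): reported change d − d = 0, so the effect is hidden.
- Effect recurs at the Week 32 +4 h ECG (e = d): reported change again 0.
- Effect is transient (e = 0 at a later pre-dose visit): reported change −d, a spurious shift in the opposite direction.

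The last case matters for vital signs, because Section 6.7.1 has them taken pre-dose only on all other dosing days. The Week 32 case matters for ECGs, because Section 6.7.4 ties post-dose ECGs to the Day 1 and Week 32 doses only.

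On placebo d = 0, so the difference between arms carries the same error of −d.

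**Step 3. Illustration.** Suppose d = 5 ms for QTcF; this is an assumed value, not one from the Protocol. The Day 1 +4 h change reads 0 instead of 5 ms. A persisting or recurring 5 ms effect reads 5 − 5 = 0 ms. A transient effect that is gone by a later visit reads 0 − 5 = −5 ms.

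**Step 4. After the fix.** With baseline taken before the first dose, the rule selects the pre-dose Day 1 vital signs (within 4 hours before dosing) and the pre-dose Day 1 ECG triplicate. Laboratory baselines stay as they are.

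**The case against.** The best counter-argument concerns scope. The baseline sentence directly follows the one on laboratory shift tables and could be read as belonging to it. For laboratory data it does no harm, since dosing-day blood is drawn before the dose. This reading is possible, but it does not rescue the section: the sentence is worded generally and is the only baseline definition there, so confining it to laboratory data leaves the ECG and vital-sign changes with no defined baseline.

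A second argument is that Section 6.3 shows what was meant. This stands in part. A reader might infer that the plan chose a post-dose baseline as a matter of analysis; the documents do not support that. Section 6.3 points to a pre-dose intention, and Section 7.2.8 itself counts adverse events from the first dose. The defect is one of wording, but the wording still gives the wrong value when followed.

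A third argument is that Section 7.2.8 leaves further details to the SAP, which is not shown and may correct this. Averaging of triplicates is indeed ordinary SAP content. The baseline rule, however, is not an omission. It is stated, and under Section 7 the SAP is to implement the Protocol's principal features, so a SAP that follows the sentence inherits the fault and one that repairs it departs from the Protocol.

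On impact, the objection largely stands. The summaries are descriptive and actual values are shown beside changes, so pre-dose and post-dose Day 1 values remain visible. Investigators review all ECGs against the Baseline visit, and ECG data are listed by patient. Section 1.5 names infections, liver function test abnormalities and injection site reactions as the important potential risks; nothing in the Protocol points to an acute effect on QTcF or haemodynamics.

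**Conclusion.** The point holds for vital signs and ECG intervals. As written, Section 7.2.8 selects a value taken 3.5 to 4.5 hours after the first dose as their baseline, against Section 6.3, in every patient with complete Day 1 assessments (about 30 by plan). The Day 1 4-hour change is then zero by construction, and every other change is off by −d.

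Three stronger readings are tempting and are not supported:

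- That the bias always runs toward no effect. This needs the acute effect to persist or recur; a transient effect gives a false change in the opposite direction.
- That all safety baselines are wrong. Laboratory changes and shift tables rest on pre-dose samples (Section 6.7.5).
- That efficacy is touched. The primary endpoint has its own baseline, the average of two valid 24-hour collections at Week −2 (Section 7.2.4).

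The size of d is unknown, and the 5 ms used above is only illustrative. The conclusion assumes that the sentence is applied literally and to ECG and vital signs. It should be corrected because it misstates two of the named safety measures and is cheap to repair, not because it threatens the trial's main result.

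**What to change.** Replace the sentence in Section 7.2.8 with:

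> Baseline is the last non-missing value obtained before the first dose of study drug; for triplicate ECGs, the mean of the predose triplicate.

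One definition can serve laboratory, ECG and vital-sign summaries alike; for laboratory data it changes nothing in practice. Where clock times are missing, use the scheduled pre-dose and post-dose labels to decide which values qualify. This matters because the Protocol explicitly requires actual times for PK blood samples (Table 5) but does not say so for vital signs or ECGs.

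The cost is one sentence in the Protocol and a matching line in the SAP. No assessment, visit or dose changes.

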### **7.2.9. Immunogenicity Analyses**

Antidrug antibody, CIC and anti-Gd-IgA1 antibody results will be summarized descriptively.

### **7.2.10. Biomarker Analyses**

Urine and serum complement activation products, inflammation and renal injury markers will be summarized descriptively.

### **7.2.11. Interim Analysis**

No formal interim analysis is planned.

### **7.2.12. Optional Additional Research**

Optional additional research may be conducted in the future on the biological samples and/or data collected during the study in accordance with the strict terms of the ICF (see Section 4.3.2).

## **8. STUDY ADMINISTRATION**

### **8.1. Ethical and Regulatory Considerations**

This study will be conducted in accordance with the protocol, all applicable regulatory requirements, and the current guidelines of Good Clinical Practice (GCP). Compliance with GCP provides public assurance that the rights, safety, and well-being of study patients are protected consistent with the principles that have their origin in the Declaration of Helsinki.

#### **8.1.1. Informed Consent**

The Investigator will ensure that the patient/legal guardian is given full and adequate oral and written information about the nature, purpose, possible risk and benefit of the study.

Patients/legal guardians must also be notified that they are free to discontinue from the study at any time. The patient/legal guardian should be given the opportunity to ask questions and allowed time to consider the information provided.

The patient's/legal guardian's signed and dated informed consent must be obtained before conducting any study tests or procedures that are not part of routine care.

The Investigator must maintain the original, signed ICF. A copy of the signed ICF must be given to the patient/legal guardian.

The Investigator will inform the patient/legal guardian if new information becomes available that may be relevant to the patient's/legal guardian's willingness to continue participation in the study. Communication of this information should be documented.

#### **8.1.2. Ethical Review**

The study protocol, including the ICF, must be approved or given a favorable opinion in writing by an IRB or IEC, as appropriate. The Investigator must submit written approval before he or she can enroll any patient into the study.

The Investigator is responsible for informing the IRB or IEC of any amendment to the protocol in accordance with local requirements. In addition, the IRB or IEC must approve all patient materials for the study (except those that support the need to remove an apparent immediate hazard to the patient). The protocol must be reapproved by the IRB or IEC upon receipt of amendments and annually, as local regulations require.

Initial IRB approval of the protocol, and all materials approved by the IRB for this study including the ICF and recruitment materials must be maintained by the Investigator and made available for inspection.

The Investigator will submit reports of SAEs as outlined in Section 6.7.6. In addition, the Investigator agrees to submit progress reports to the IRB or IEC per their local reporting requirements, or at least annually and at the conclusion of the study. The reports will be made available to the Sponsor or designee.

Any communications from regulatory agencies, IRBs, or IECs in regard to inspections, other studies that impact this protocol or the qualifications of study personnel should be promptly reported to the Sponsor or its designee.

The Investigator is also responsible for providing the IRB with reports of any reportable serious adverse drug reactions from any other study conducted with the study drug. The Sponsor or designee will provide this information to the Investigator.

Major changes in this research activity, except those to remove an apparent immediate hazard to the patient, must be reviewed and approved by the Sponsor and the IRB or IEC that approved the study. Amendments to the protocol must be submitted in writing to the Investigator's IRB or IEC and the Regulatory Authority for approval before patients are randomized under the amended protocol, and patients must be re-consented to the most current version of the ICF.

### **8.1.3. Serious Breach of Protocol**

Investigators must notify the Medical Monitor within 24 hours of becoming aware of a serious breach of the protocol. A serious breach is a breach that is likely to affect to a significant degree the safety and rights of a study participant or the reliability and robustness of the data generated in the clinical trial.

### **8.1.4. Study Documentation, Confidentiality, and Records Retention**

All documentation relating to the study should be retained for 2 years after the last approval in an ICH territory or as locally required, whichever is longer. If it becomes necessary for the Sponsor, the Sponsor's designee, applicable IRB/IEC, or applicable regulatory authorities to review or audit any documentation relating to the study, the Investigator must permit direct access to all source documents/data. Records will not be destroyed without informing the Sponsor in writing and giving the Sponsor the opportunity to store the records for a longer period of time at the Sponsor's expense.

The Investigator must ensure that the patients' confidentiality will be maintained. On the eCRFs or other documents submitted to the Sponsor or designees, patients should not be identified by their names, but by the assigned patient number or code. If patient names are included on copies of documents submitted to the Sponsor or designees, the names will be obliterated, and the assigned patient number added to the document. Documents not for submission to the Sponsor (eg, signed ICFs) should be maintained by the Investigator in strict confidence.

The Investigator must treat all information related to the study and the compiled data as confidential, whose use is for the purpose of conducting the study. The Sponsor must approve any transfer of information not directly involved in the study.

To comply with local and/or regional regulations, this clinical study may be registered, and study results may be posted on public registries, such as ClinicalTrials.gov.

